# **Power Analysis**

For an fMRI study of cognitive function, Desmond and Glover [29] reported that about 25 subjects are necessary to achieve 80% power for a 0.5% increase of activity. We also conducted power analysis based on our previous study with graded sedation of propofol [30]. The average Cohen's d as a measure of the effect size was 0.56. For 80% power and  $\alpha$ =0.05, N=24 human subjects will be needed. The obtained subject number is also very close to the suggested optimal group size for reliable statistics in functional MRI studies [31]. We plan for a minimum of 25 subjects per group.

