We will calculate the average BOLD activity (across the trials with real images) in the regions of interest including the CT, AIC, and DLPFC. For a given measurement, repeated-measures ANOVA plus post-hoc tests will be performed at the group level. Inter-subject multivariate linear regression analyses will be performed with SDT metrics as dependent variables and average BOLD activity as independent variables. Statistical significance will be defined at FDR-corrected  $\alpha < 0.05$ .

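### The sample size is powered at one unadjusted alpha of 0.05, but significance is decided after FDR correction, so the stated 80% is not the power of the test that will be run

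*Combined protocol and SAP*

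**What the plan says.** Power Analysis rests the group size partly on the team's earlier graded-sedation study: "The average Cohen's d as a measure of the effect size was 0.56". With 80% power and an alpha of 0.05 it finds that "N=24 human subjects will be needed", and then states: "We plan for a minimum of 25 subjects per group". It mentions no multiplicity adjustment. It also cites a published fMRI sample-size study and a paper on group size as support for a number near 25.

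The BOLD response is the primary outcome. Data Analysis and Statistics averages it "in the regions of interest including the CT, AIC, and DLPFC" and says that "repeated-measures ANOVA plus post-hoc tests will be performed at the group level". It then describes regressions of the signal-detection metrics on BOLD activity, and closes with the decision rule: "Statistical significance will be defined at FDR-corrected" 0.05. It does not name the FDR procedure, the set of tests corrected together, or whether tests are one- or two-sided.

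The section on number of subjects plans 100 evaluable participants in four groups. It enrols 150 to allow for unevaluable participants, which does not raise the evaluable number per group.

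**The concern.** Power belongs to a test at a stated threshold. Here the threshold in the power calculation is a single 0.05, while the threshold that decides significance is lower for at least some of the tests. If 25 per group was chosen to give 80% power at the first threshold, it gives less at the second.

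The stake is interpretation. A region-level null result in a group of 25 would be read against a claimed 20% chance of missing a true effect of d = 0.56. Under the FDR rule that chance could be near 40%, depending on choices the plan has not made.

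**Working it through.** **Inputs.** From Power Analysis: d = 0.56, power 80%, alpha 0.05, N = 24, 25 per group. From Data Analysis and Statistics: FDR-corrected 0.05 and at least three regions (CT, AIC, DLPFC). Assumed, because the documents are silent: Benjamini-Hochberg as the FDR procedure, the three regions as the family, d = 0.56 in each responding region and zero elsewhere, between-region correlation of 0, 0.5 or 0.8, and sidedness (both shown).

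**1. The plan's own figure.** For one paired test, n = ((z_alpha + z_power)/d)².
- Two-sided normal: ((1.960 + 0.842)/0.56)² = 25.03, rounded up to 26. Paired t: 28.
- One-sided normal: ((1.645 + 0.842)/0.56)² = 19.71, rounded up to 20. Paired t: 22.
- Two-sample comparison, two-sided: 51 (normal) or 52 (t) per group.

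No variant gives exactly 24. The nearest are 22 and 26, both for a single within-subject test at an unadjusted 0.05. A between-group calculation is far off.

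**2. Power at n = 25 before correction.** The noncentrality is 0.56 × √25 = 2.80 on 24 degrees of freedom. Two-sided at 0.05 the critical t is 2.064 and power is 76.6% (80.0% by the normal approximation). One-sided it is 85.9%.

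**3. The strictest FDR step for three tests.** At 0.05/3 = 0.0167, two-sided, the critical t is 2.574 and power is 59.4%. This approximates the case where one region responds.

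**4. Benjamini-Hochberg over three regions, n = 25, by simulation.** Entries are average power per truly responding region, over the three correlations.

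| Regions with d = 0.56 | Two-sided | One-sided |
|---|---|---|
| One | about 60% | about 71% |
| Two | about 67% | 78–79% |
| All three | 71–74% | 82–84% |

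**5. Detectable effect at 80% power, n = 25, two-sided.** d = 0.58 at 0.05 and d = 0.69 at 0.05/3.

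**6. Pooled contrast.** Baseline versus sedation is measured in all 100 evaluable subjects. The noncentrality is 0.56 × √100 = 5.6, and power is 99.9% even at 0.05/3.

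**The case against.** Five objections carry weight.

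- **The family is not fixed.** The FDR rule follows a sentence on ANOVA with post-hoc tests and another on regressions. It could apply to the contrasts within one measurement, to the regions or to the regression coefficients. Three regions is a reasonable reading, not a stated one. This stands, so the loss is conditional.
- **The hypotheses are directional.** One-sided tests with all three regions responding give 82–84%. This stands as an exception, although the documents never state one-sided testing and ANOVA F-tests are non-directional.
- **FDR does not cause the whole gap.** The two-sided paired t-test has 76.6% before correction, about 3 points below 80%. If all three regions respond, FDR removes only a few points more.
- **The definition of power matters.** The chance of detecting at least one of three responding regions is about 78–95% two-sided, so a plan that needed only one would look better.
- **The effect size comes from sedation.** The matching contrast is baseline versus sedation. Pooled over 100 subjects it is safe; the shortfall concerns tests within a group of 25.

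A reader might also take 60% as the plan's own expected case, because Anticipated Results and Interpretation names only the DLPFC when it predicts the BOLD effect of DLPFC stimulation. The text does not support that. It does not say that the other regions stay unchanged; its no-change prediction there concerns d'. For sedation it expects reductions in every region examined, and for CT stimulation a broad increase.

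The two other sources cited for about 25 subjects do not settle the matter, since the documents do not show whether they allow for multiplicity.

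**Conclusion.** The mismatch holds: the powered threshold is not the deciding one, and nothing in the plan connects them. Its size depends on choices the plan leaves open. With a three-region family, Benjamini-Hochberg and d = 0.56, average per-region power for a within-group paired contrast at n = 25 is about 60–74% two-sided and about 71–84% one-sided. Of the cases examined, only one-sided testing with all three regions responding reaches 80%.

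Two stronger conclusions should not be drawn. One is that 25 per group falls short under every reading; the one-sided case and the pooled contrast show otherwise. The other is that these figures describe the randomised LIFUP-versus-sham comparison. They do not: that is a two-sample contrast, with about 49% power at the same d with 25 per group before any correction, and it is a separate question.

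This is a correction to a stated property of the design that should be made. It is not a reason to change the design.

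**What to change.** Keep the sample size. In Power Analysis, name the FDR procedure and family, the sidedness and the contrast being powered, and restate the power at that threshold. If the family is the three regions and tests are two-sided, the text could read:

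> For a within-group paired contrast with 25 subjects and d = 0.56, two-sided, average power per region after Benjamini-Hochberg FDR correction over three regions (CT, AIC, DLPFC) is about 60–74%, depending on how many regions respond; d = 0.69 is detectable with 80% power if only one does. This is not the power of the between-group comparison of LIFUP with sham.

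If the team chooses another family or one-sided tests, the figures must be recomputed for that choice, and Data Analysis and Statistics should carry the same definition. The cost is a sentence or two and a less favourable power figure, with no extra subjects.

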# **Number of Subjects, Recruitment and Informed Consent**

Statistical power analysis (see below) requires a group of 25 subjects. We plan to enroll 100 evaluable subjects randomly assign into four groups; we intend to enroll 150 subjects to account for unevaluable participants. See experimental design details below. Healthy participants will be recruited by listing on UMClinicalStudies.org and by postings at area colleges and community groups in Ann Arbor. Interested volunteers will call the phone number of a designated recruiter for an initial phone screening. The initial phone screening will consist of questionnaires related to medical history, demographic information, handedness, inclusion and exclusion criteria and procedure standard MRI screening questionnaire. If interested, the participant will complete the questionnaires, which will be reviewed by the study team. The health status will be confirmed by the attending anesthesiologist before the study on site. Once eligibility is confirmed by the study team, the one-time research study session will be scheduled. Participants will screened for COVID-19 prior to entry into the hospital per hospital guidelines. A standard face mask will be provided upon hospital entry if participants do not have one.

All participants will give written informed consent according to institutional guidelines prior to any testing. The Principal Investigators or their designee will obtain consent using a written consent form approved by the Institutional Review Boards of the University of Michigan Medical School (IRBMED). It will contain detailed information regarding the purpose, risks and benefits of participating. Copies of the signed consent form will be given to the subjects; the original consent will remain with the study team. Subjects will be compensated for their involvement.

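### The 80% power behind 25 per group belongs to a sedation effect and does not carry over to the randomised LIFUP-versus-sham comparison, for which no effect size or detectable difference is given

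*Combined protocol and SAP*

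**What the plan says.** The Power Analysis section ends with the group size, "We plan for a minimum of 25 subjects per group", and gives three supports for it.

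- A published fMRI figure: "about 25 subjects are necessary to achieve 80% power for a 0.5% increase of activity".
- The sponsor's own calculation: "We also conducted power analysis based on our previous study with graded sedation of propofol". It continues: "The average Cohen's d as a measure of the effect size was 0.56", and at 80% power and alpha 0.05, "N=24 human subjects will be needed". The test, its sidedness and the type of Cohen's d are not stated.
- Closeness to a "suggested optimal group size for reliable statistics in functional MRI studies", with no effect size attached.

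The section on number of subjects carries this forward: "Statistical power analysis (see below) requires a group of 25 subjects", then "We plan to enroll 100 evaluable subjects randomly assign into four groups".

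Under Experimental Design, every subject has a wakeful baseline session, then a sedation session, then a sedation+LIFUP session, in that order. Randomisation decides only whether LIFUP goes to DLPFC, AIC or CT, or is sham.

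The primary outcome is the BOLD response; criterion c and sensitivity d' are secondary. Data Analysis and Statistics plans a repeated-measures ANOVA with post-hoc tests at FDR-corrected 0.05 and names no LIFUP contrast. Anticipated Results and Interpretation gives LIFUP effects by direction only. DLPFC stimulation should raise c but leave d' alone, AIC stimulation the reverse, and CT stimulation should raise both and arguably bring performance back to baseline.

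**The concern.** The power statement and the randomised question concern different effects. The sedation effect is a within-subject contrast of baseline with sedation. It occurs before any LIFUP is given, so all 100 evaluable subjects can contribute to it. A group size of 25 therefore limits only the LIFUP contrasts, and for those the plan gives no basis.

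A within-group change from sedation to sedation+LIFUP mixes any LIFUP effect with elapsed time under propofol, because the order of sessions is fixed. The sham group is there to separate the two, so the causal claims about CT, AIC and DLPFC rest on comparisons between randomised groups. Those comparisons are less precise than a within-subject one of the same nominal size. A reader who takes 80% power to apply to them would expect more from the trial than the plan supports, for BOLD as well as for c and d'.

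**Working it through.** **Inputs from the Power Analysis section:** d = 0.56, power 80%, alpha 0.05, N = 24, 25 per group. **Assumed here:** two-sided tests, no FDR correction unless stated, and correlation r between a subject's sedation and sedation+LIFUP values of 0.3, 0.5 or 0.7, with equal variances. The documents give no correlation.

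**1. Reproducing N = 24.**
- One group, paired, normal approximation: n = ((1.960 + 0.842)/0.56)² = 25.03, so 26. Exact paired t: 28; power at n = 24 is 74.8%.
- One-sided: 20 (normal) or 22 (exact t).
- Two groups, normal: n = 2 × 25.03 = 50.06, so 51 per group. Exact t: 52 (41 one-sided).

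No variant gives exactly 24. The paired figures come close; the two-group figures are about twice as large.

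**2. What 25 gives for each contrast (noncentral t).**

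| Contrast | 80% power at | Power at 0.56 SD of the change |
|---|---|---|
| Baseline vs sedation, n = 100 | 0.28 SD of the change | – |
| Within-group change, n = 25 | 0.58 SD of the change | 77% |
| Active vs sham, change scores, 25 vs 25 | 0.81 SD of the change | 49% |

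For the last row the noncentrality at 0.56 is 0.56 × √(25/2) = 1.98 on 48 df. The 95% CI half-width is 2.011 × √(2/25) = 0.57 SD of the change.

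**3. Effect of adjusting for the sedation-session value (ANCOVA, 47 df).** With raw SD σ, the change has SD σ√(2(1−r)) and the ANCOVA residual has SD σ√(1−r²). An effect of d in change-SD units is therefore multiplied by √(2/(1+r)). An effect of d in raw-SD units becomes d/√(1−r²) under ANCOVA and d/√(2(1−r)) for change scores.

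| r | Power at 0.56 change-SD: change score → ANCOVA | Power at 0.56 raw-SD: change score → ANCOVA | ANCOVA, 80% power at: change-SD / raw-SD |
|---|---|---|---|
| 0.3 | 49% → 67% | 37% → 53% | 0.65 / 0.77 |
| 0.5 | 49% → 61% | 49% → 61% | 0.70 / 0.70 |
| 0.7 | 49% → 56% | 71% → 77% | 0.75 / 0.58 |

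These are formula values. Simulation of the change-SD column gave 66%, 60% and 55%. The two scales move in opposite directions as r rises, so both are shown.

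**4. Multiplicity.** FDR correction makes these figures less favourable. For a family of three active-versus-sham contrasts (assumed), Bonferroni gives the pessimistic end, since the Benjamini-Hochberg procedure rejects whatever Bonferroni rejects. At alpha 0.0167, unadjusted change scores reach 80% power at 0.94 SD of the change, with 32% power at 0.56.

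**The case against.** **The trial may be adequately powered.** No LIFUP effect size is given, so nothing here shows otherwise. A reader might infer from the 49% that the trial is underpowered; the documents do not support that. The 0.56 is a sedation effect on an unstated scale. Its one link to LIFUP is the prediction that CT stimulation restores performance to baseline, which implies an effect about as large as sedation's. That covers CT only, and the Power Analysis section does not use it. In raw-SD units with r = 0.7, power at 0.56 is 71% even unadjusted.

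**N = 24 may come from the planned ANOVA.** With f = 0.28, three sessions and four groups (all assumed), a repeated-measures calculation gives a total of 23 for the session effect at r = 0.5, or 21 for the group-by-session interaction at r = 0.7. So N = 24 should not be called an arithmetic error. The input would still be a sedation effect, and the plan does not say which calculation was run.

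**The planned ANOVA can already contain the contrast.** A group-by-session term and target-versus-sham post-hoc tests are compatible with the text, and the documents do not name active versus sham as the primary contrast. That stands. But nothing says which post-hoc test answers the LIFUP question.

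**The predictions of no change are only expectations.** A reader might infer that non-significance will be taken as absence of effect. No section says so. What remains is that the plan names no way to support those predictions.

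**Conclusion.** The concern holds in a limited form. The stated 80% power applies at most to a within-subject sedation effect and does not carry over to the randomised comparison. For active versus sham, 25 per group gives 80% power at about 0.81 SD of the change unadjusted, or 0.65 to 0.75 SD of the change (0.77 to 0.58 raw SD) with ANCOVA, for r from 0.3 to 0.7, two-sided and before FDR.

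The absence of any LIFUP effect size or detectable difference can be read directly from the plan and needs no assumption. The 0.81 needs only the usual normal-theory conditions. Every power figure at 0.56 depends on borrowing the sedation effect and choosing its scale, and every ANCOVA figure on an assumed correlation. Whether 25 per group suffices cannot be settled from the documents.

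**What to change.** Enrolment and measurements stay as they are.

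1. **Data Analysis and Statistics.** Name the deciding LIFUP test in place of the unspecified post-hoc tests for that question: each active target versus sham on the sedation+LIFUP value, adjusted for the same subject's sedation-session value (ANCOVA). Define the three contrasts per measure as the FDR family and report 95% CIs. Keep the repeated-measures ANOVA for session effects, so that one analysis decides each question.
2. **Power Analysis.** State the test and sidedness behind N = 24, and limit that power statement to the within-subject sedation effect. Add that active versus sham (25 vs 25, ANCOVA, two-sided, before FDR) has 80% power for about 0.77, 0.70 or 0.58 raw SD (0.65, 0.70 or 0.75 SD of the change) at assumed session correlations of 0.3, 0.5 or 0.7, and that FDR correction makes this less favourable. If the sponsor has an expected LIFUP effect, put it beside these figures.
3. **Anticipated Results and Interpretation.** Say that the predicted absence of change in d' (DLPFC) or c (AIC) will be judged from the CI and not from a non-significant test.

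The cost is a revised paragraph, one named contrast and CI reporting. The downside is a less favourable stated power for LIFUP, and a precision gain that depends on a correlation the protocol does not give.

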# **Biological Variables**

We will recruit participants of both sexes with various ethnic/racial backgrounds, aiming for diversity and equal representation. The age range will be limited to 18-40 years in order to limit age-dependent variation in anesthetic requirement for sedation and for participant safety.

# **Human Studies and Safety Profile related to LIFUP**

The first human application of the LIFUP technique targeted the primary somatosensory cortex of healthy volunteers in a sham-controlled study [32]. Subsequently, low-intensity ultrasonic thalamic stimulation was successfully applied to facilitate the emergence of a patient from minimally conscious state after acute brain injury [25]. This was followed up by the recent report on the same subject [24] and ongoing clinical trial for thalamic low-intensity focused ultrasound modulation of consciousness following in brain injury (Nct02522429; https://clinicaltrials.gov/ct2/show/NCT02522429).

LIFUP has important advantages over formerly applied interventions that makes it a highly promising clinical tool. Compared to existing magnetic or electric noninvasive brain stimulation, LIFUP provides superior spatial resolution on the millimeter scale as well as the capability to target sub-cortical structures non-invasively. Because of LIFUP' high spatial resolution and ability to stimulate at depth, it is also of particular interest to pair with concurrent magnetic resonance imaging (MRI) that helps both precise targeting and readout of the stimulation effects.

The biophysical mechanism of LIFUP is not fully understood; several mechanisms including mechanically induced changes in membrane capacitance, cavitation events, and mechanical sensitivity of voltage-gated ion channels [33,34] have been proposed. Currently, the ion channel modulation theory seems to be most plausible [33,35]. Although a few studies reported inhibitory effects of LIFUP on visual-evoked potentials in animals [36,37] and somatosensory-evoked potentials in humans [32], the majority of LIFUP studies have reported motor or sensory effects consistent with neural excitation (a recent review by [38]).

The application of LIFUP over 0.5–5 min has been shown to produce persistent neuromodulatory effects, lasting from a few minutes to several hours. For example, excitation-like effects and changes in functional connectivity lasting for over an hour were reported in nonhuman primates and human subjects. Stimulation of the amygdala and supplementary motor area in nonhuman primates affected circuit connectivity, resulting in a change in coupling of fMRI activity between the LIFUP target and other brain areas [39,40]. LIFUP stimulation of the frontal eye field of macagues for 100 ms immediately before a visual cue shifted the bias of a choice task in favor of

the corresponding contralateral side [41]. The forgoing evidence supports the feasibility and potential effectiveness of LIFUP to modulate circuitry of interest.

LIFUP has been shown to be a safe and effective method to modulate human brain activity, when the stimulation parameters and protocol follow the available guidelines [38,42,43]. The majority of studies with ultrasound have reported no adverse events or evidence of anatomical damage [32,44–47]. Mild and moderate symptoms were reported such as neck pain, sleepiness, muscle twitches, itchiness, and headache [48,49]. An in-depth survey of the safety of ultrasound for human neuromodulation did not find any evidence of serious events in a large cohort of participants [50]. Specifically, 64/120 participants (53%) responded to follow-up questionnaire, and none of them experienced serious adverse effects. 7/64 reported mild to moderate symptoms (e.g., neck pain, problems with attention, muscle twitches and anxiety), that were perceived as 'possibly' or 'probably' related to participation in LIFUP experiments. The most common unrelated symptoms included sleepiness and neck pain. There were initial transient reports of mild neck pain, scalp tingling and headache that were extinguished upon follow-up. No new symptoms were reported upon follow up out to 1 month [50]. In addition, no studies have shown LIFUP induced tissue damage in the absence of heating, unless they utilized contrast agents to enhance cavitation effects [34]. Finally, the LIFUP appears to be safe even at intensities several times higher than the FDA limit for diagnostic ultrasound (720 mW/cm^2) [51].

# Potential Risks related to MRI Scanning

There are no known risks associated with magnetic resonance imaging, as long as technical parameters remain within FDA guidelines. A licensed MR technologist is instructed in these guidelines and performs all machine manipulations. Complete histories, physical examinations and stringent medical guidelines exclude many potential subjects before they enter the study, thereby further minimizing risks. A crash cart is always present and regular safety drills are performed by the medical and experimental staff to prepare for any untoward effects.

MRI Static Magnetic Fields: FDA guidelines for clinical product scanners limit the main magnetic field to 3 Tesla. Our studies will be performed on a standard, clinical 3 T Philips scanner. A substantial body of literature exits that supports the safety of field strengths up to 7 T. There are no known risks of exposure to 3 or 7 T fields for MR imaging.

Among the reported biological effects of exposure to strong static magnetic fields are the following: 1) Dizziness (with nausea) or stimulation of the sensory nerves in the soft palate has been reported as a result of the subject's head being moved while in the magnet. 2) Rapid eye movement has been reported (at 4 and 7 T) to cause magnetophosphene effects. First described in 1896, these flickering light sensations are similar to visual phenomena caused by direct electric current passage across the head or retina.

Radiofrequency (rf) Magnetic Fields: Radiofrequency energy burns are the result of high electric fluxes in the immediate vicinity of the patient. All MRI systems create some rf electric fields incidental to the production of the intended rf magnetic fields. The potential causes are malfunctions in the rf coil switching circuitry, improper use of the surface coils, design flaws in some clinical MRI system surface coils or cardiac gating patient connection leads. Nationally, 60 burn incidents have been reported to the FDA in the course of approximately 11 million exams. Our site has never experienced any difficulty in this regard.

Acoustic Noise: The sound generated by an MR system usually consists of a series of repetitive pulses. The relevant safety parameters required to characterize such a noise are the peak impulse sound pressure level (Lpeak) and the time integral of the A-weighted sound pressure level (Leq). In MR applications, the peak impulse sound pressure level is dependent upon the peak amplitude of the individual pulses, while the time integral of the A-weighted sound pressure

level is dependent upon the continuous exposure to a series of such pulses. Acoustic noise is a result of the mechanical vibration produced by the gradient coils when the nominally large currents are applied to them to create time varying imaging gradient fields. The sound produced can be loud enough to produce temporary deafness (up to 95 dB). Foam earplugs will attenuate this noise by up to 30 dB. They are in routine use at the 3T systems, and have been proven effective.

*Claustrophobia:* While inside the magnet, subjects may experience an acute panic attack due to claustrophobia. Subjects are all prescreened for fear of tight places. Once inside the magnet, the subject will be given a squeeze ball to signal the MR operator if he or she is under acute distress.

